8.0 PRETREATMENT EVALUATION

Any time prior to treatment start

- Review of all prior external beam radiation therapy (dose volume histograms, beam arrangement, and port films required)
- MSKCC pathology review

Within 3 months prior to treatment start

- History and physical
- KPS
- Baseline pain assessment
- Assessment of baseline comorbidities
- Conmed review

Within 30 days prior to treatment start

- CBC, Comprehensive Serum Chemistry, INR/PTT
- MRI if not otherwise contraindicated
- CT scan without contrast in the prone position (optional if supine CT already performed)
- Standard preoperative workup

Within 2 weeks prior to treatment start

- Pregnancy test for women of childbearing potential

9.0 TREATMENT/INTERVENTION PLAN

All eligible patients will be approached for enrollment. Patients enrolled on the protocol will be scheduled for brachytherapy as per routine, including all necessary laboratory tests for preadmission testing as currently practiced.

Prior to procedure :

1. Patient radiographic scans (CT and/or MRI) will be reviewed by the physicians prior to the HDR catheter placement procedure to determine the optimal catheter placement trajectories.

HDR Catheter Placement using image-guided navigation:

The procedure is as currently performed with the addition of the optical fiducial placement and registration to the Medtronic STEALTH® system; fiducial placement, image acquisition, and image registration is expected to add 10-20 minutes to the procedure.

1. The patient will be intubated following induction of anesthesia.
2. The patient will be positioned in the prone position and prepped.
3. An optical fiducial will be placed in the patient for registration with the Medtronic STEALTH system (either mounted on a spinous process near the treatment site or on a post fixed to the iliac crest through a stab incision).
4. A fine-slice (~1mm thick slices with 1mm spacing) cone-beam/O-arm CT scan will be obtained and registered to the Medtronic STEALTH® system.
5. Catheters will be placed under Medtronic STEALTH® guidance, either into the vertebral bodies/ paravertebral tissues or pelvic tissues. Placement will be based upon size and location of the lesion, proximity to critical structures, and hardware already present in the patient (i.e.: post-surgical fixation and stabilization). Where possible, it is preferred to keep the catheters at least 5mm apart. Catheters will be placed such that they will extend to the anterior portion of the vertebral body where applicable; spatial information of all catheters will be used to avoid overlap and/or collision during placement.
6. Depth of placement will be verified with fluoroscopic images and a repeat O-arm CT scan will be taken.
 - a. As with the pre-placement CT scan, image slices should be ~1mm thick with 1mm spacing.
 - b. Field of view of the CT scan must encompass the tips of each catheter as well as the buttons used to secure the catheters to the skin; Teflon filaments will be left in the brachytherapy catheters during the scan.
 - c. Each catheter filament will be marked and labeled with depth of insertion into the catheter.
 - d. Final setup picture with catheters in place will be taken and placed in the patient's treatment chart.

Treatment planning: as currently performed without new devices or techniques.

1. Intraoperative CT scans will be transferred to our treatment planning system (Brachyvision) with the assistance of Brachytherapy Physics:
 - a. Catheter positions will be digitized for planning by Brachytherapy Physics.
 - b. The vertebral body/paraspinal tissue and/or pelvic lesion will be contoured to provide the gross target volume (GTV), as well as a clinical target volume (CTV) to encompass potential microscopic disease; in some cases the GTV = CTV, at the discretion of the planning radiation oncologist.
 - c. Associated critical structures that have received significant prior radiation dose such as esophagus, bowel, kidneys, and rectum will be contoured and appropriate dose constraints will be applied as per standard practice. In all cases the spinal canal, cord and/or cauda will be contoured.
2. The final treatment plan will be generated by Brachytherapy physics based on the post-placement images utilizing computer optimized three dimensional treatment planning.

MEMORIAL SLOAN-KETTERING CANCER CENTER IRB PROTOCOL #: 12-260 A(4)

- a. The following dose constraints will be used for treatment planning:
 - i. Prescribed dose is 14 Gy to the periphery of the GTV.
 - ii. GTV coverage by the prescription dose will at least be 80% (D90 \geq 80%).
 - iii. Maximum cord dose (cord Dmax) will be 8 Gy.
 - iv. For lesions in close proximity (<5cm) to visceral organs, the relevant constraints will be applied:
 1. Esophagus max dose (esophagus Dmax) will be 9 Gy.
 2. Kidney max dose (kidney Dmax) will be 11 Gy.
 3. Bowel/Rectum max dose (bowel/rectum Dmax) will be a BED Gy equivalent of 85 Gy in 2 Gy fractions (accounting for all prior treatment).
3. Plan will be reviewed and approved by the radiation oncologist.
 - i. If the target dose of 14 Gy to the GTV cannot be met without exceeding dose constraints to the cord and other organs-at-risk, the highest achievable dose will be delivered that does not exceed dose constraints to organs at risk (spinal cord/cauda, esophagus, kidney, or bowel).
4. The treatment plan will undergo quality assurance procedures as per routine.

Treatment delivery and completion of care: as currently performed without new devices or techniques.

1. The HDR unit is attached to the brachytherapy catheters and catheter positioning is verified using a combination of KV fluoroscopic images as well as checking individual catheter depths with marked filaments.
2. HDR brachytherapy is delivered in the HDR procedure room as per routine.
3. After completion of treatment, all HDR catheters will be removed with the assistance of Neurosurgery and bandages will be applied.
4. Patient will be monitored for a minimum of 1 hour after catheter removal and then discharged home if appropriate.
5. Patients will undergo deep venous prophylaxis and pain management throughout the course of treatment as per routine.

10.0 EVALUATION DURING TREATMENT/INTERVENTION

Dosimetric planning will be performed on pre-implantation planning CT and then merged with post-implant CT images obtained following catheter placement. Specific dosimetric parameters will include GTV V90, V100, V150, V200, D90, and cord/cauda dose volume histograms. Treatment complications will be monitored in terms of radiation related toxicity during post-procedure recovery and during followup visits; all patients treated on this protocol will be evaluated regardless of whether dosimetric goals were met.

Regular follow up visits will be scheduled at 2 months (+/- 2 weeks) and then at 3 month (+/- 2 weeks) intervals until approximately 11 months of follow up. During these follow up visits, standard evaluations currently performed on all spine and/or pelvic radiation therapy patients (physical examination and imaging) will be performed. Thus, no activities that are not currently billed will be necessary. Follow up after 1 year will be performed as per standard clinical practice with no further protocol obligations.

If after the 2 month follow up a patient is not available to come in for a follow up visit, a telephone follow up by a clinical investigator will be allowed for up to two of the remaining follow up visits. If a phone call follow up is used, the physical exam will be foregone. Outside imaging studies are also allowed but must be reviewed at MSKCC.

	Screening	Treatment	Follow up (2 months post-treatment, then every 3 months until approximately 11 months of follow up)
Review of pathology	X		
Review of prior treatment	X		
Medical history	X		
Physical Exam, including neurological assessment and ambulation assessment	X		X
KPS	X		
CBC	X		
Comprehensive Serum Chemistry	X		
INR/PTT	X		
CT spine or pelvis ¹ (without contrast)	X ²	X	X ³
MRI spine or pelvis ¹ (unless contraindicated)	X		X
Pre-operative workup	X		
AE assessment	Baseline comorbidities		X
Pain assessment	X		X
Review of Commeds	X		
Pregnancy test	X		
HDR		X	

1 Imaging location will be dependent on the lesion site of interest

2 CT scan in prone position is required unless a supine CT has already been performed within 30 days of planned treatment

3 Optional if MRI is performed

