1.0 PROTOCOL SUMMARY AND/OR SCHEMA

This pilot study is an investigation into the use of Ir-192 high dose rate (HDR) afterloader-based brachytherapy with catheter placement using image-guided surgical navigation techniques for patients with painful/symptomatic metastatic or recurrent lesions in the spine and/or pelvis that have been maximally treated with external beam radiation therapy. This study will assess the feasibility of this approach in terms of appropriate dosimetric coverage of the target volume with sparing of tissues/organs at risk from excessive radiation dose.

Patients enrolled on this study will undergo HDR brachytherapy using the same equipment, techniques and treatment planning aspects as currently practiced at MSKCC, with the exception of the incorporation of image-guided surgical navigation equipment into the HDR catheter placement procedure.

Patients will be followed at 2 months (+/- 2 weeks) post-treatment and then approximately every 3 months (+/- 2 weeks) until approximately 11 months of follow up. They will be evaluated for pain referable to the treated site, clinical and radiographic evidence of local progression, and treatment related toxicity. Thereafter, patients will be followed as clinically indicated.

Twenty patients will be entered into this protocol which is expected to take 4 years to complete.

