3.0 BACKGROUND AND RATIONALE

Current treatment regimens at MSKCC for metastatic and primary lesions in the spine and paraspinal lesions of the pelvis include a range of external beam fractionation schedules, ranging from conventional low-dose-per-fraction (high total dose) treatments extending over many weeks to high dose single-fraction treatments delivered in a single day. Conventional external beam therapy has been shown to achieve local control rates range less than 50%. [Greenberg 1980, Maranzano 1998, Klekamp 1998] In contrast, advances in stereotactic external beam radiation therapy have improved local control of lesions in the spine to >90% using high-dose single fraction treatments as initial therapy. [Yamada 2008, Moulding 2010] For the subset of patients who progress locally after optimal treatment, local control may be difficult or impossible to salvage with additional external beam radiation therapy due to limits of normal tissue tolerance to radiation, particularly that of the spinal cord.

The generally accepted dose limit for the spinal cord is 45 Gy at 1.8-2.0 Gy/fraction (Schultheiss 1995); 50 Gy is observed in otherwise healthy patients treated with curative intent where the tumor location prohibits limiting the cord to a lower dose, with an attendant 5% risk of myelopathy at 5 years. [Emami 1991, Schultheiss 1995] For patients undergoing high-dose spinal cord radiosurgical procedures, spinal cord tolerance is defined as a cord maximal dose of 14 Gy, or less than 10 Gy to 10% volume of the spinal cord per level. [Ryu 2007, Yamada 2008] In the event of failure, these limitations may preclude or impair the ability of radiation oncologists to offer effective salvage therapy with external beam techniques. Toxicity resulting from repeat irradiation is a subject of open investigation, with thresholds of 100-135 BED Gy equivalent proposed for late complications due to repeat irradiation of the spinal cord. [Rades 2005, Nieder 2005, Sahgal 2012] (BED Gy equivalent is determined by the biological equivalent dose (BED) calculation; $BED = nd(1 + d/\alpha/\beta)$, where n = number of fractions and d = dose per fraction; α/β is the constant for spinal cord late effect and equals 2.)

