11.0 TOXICITIES/SIDE EFFECTS

For non-serious adverse events, we will only be capturing the toxicities that are possibly related to protocol treatment. The National Cancer Institute (NCI) Common Terminology Criteria for Adverse Events (CTCAE) version 4.0 will be used as an instrument to evaluate toxicities, discussed in section 12.

The toxicities associated with radiation therapy to the spine or pelvis can be classified as either early (occurring within 90 days of the treatment) or late toxicities (after 90 days to 1 year). Mild acute toxicities that are expected from treatment include Grade 1-2 fatigue and irritation at the sites of catheter insertion, as well as a generally transient pain flare in the treated bone site. Less likely (<5% of the time) would be infection or bleeding at the sites of catheter insertion. Rare but serious (<1%) acute toxicities could include complications such

MEMORIAL SLOAN-KETTERING CANCER CENTER IRB PROTOCOL #: 12-260 A(4)

as perforation of a visceral organ during catheter placement (lung, bowel, or kidney) or fractures in the bones of the spine.

There are two types of toxicity which will be considered as potentially serious adverse events from the brachytherapy treatment: neurologic and musculoskeletal. These generally occur late and include myelitis or pathologic fractures of the bones of the spine and/or pelvis. Neurologic and musculoskeletal toxicities will be evaluated with the National Cancer Institute (NCI) Common Toxicity Criteria v4.0 (discussed in section 12, also see Appendix 2 for specifics). The probability of severe (\geq grade 3) neurologic and musculoskeletal toxicity is expected to be less than 10%, which is below the currently observed rate of severe toxicity reported by patients who undergo standard radiation therapy for lesions of the spine at MSKCC.

DEFINITIONS

1. Definition of an Adverse Event (AE)
 - a. An Adverse Event is defined by the GCP (Guide to Good Clinical Practice) as any undesirable experience occurring to a subject during a clinical trial, whether or not it is considered related to the investigational product(s). In this trial we will only document those AEs that are at least possibly related to protocol therapy.
2. Definition of a Serious Adverse Event (SAE)
 - a. A Serious Adverse Event is an adverse experience that:
 - i. is fatal or life-threatening
 - ii. is disabling

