12.0 CRITERIA FOR THERAPEUTIC RESPONSE/OUTCOME ASSESSMENT

Review of dosimetric characteristics of the patients' treatment plans will be performed to determine if the treatments were able to adequately meet determined parameters.

The primary objective of the study is to validate the feasibility of HDR treatment of spine and pelvic lesions using catheters placed under image-guided navigational techniques:

1. This will be accomplished by the following criteria: We consider a D90 of $\geq 80\%$ for the lesion GTV with cord and/or cauda equina maximum doses ≤ 8 Gy as acceptable dosimetric endpoints. Dosimetry will be evaluated following implantation of

MEMORIAL SLOAN-KETTERING CANCER CENTER IRB PROTOCOL #: 12-260 A(4)

brachytherapy catheters and prior to patient treatment.

The secondary objectives concern toxicity and clinical outcomes, and will be evaluated regardless of whether the primary objective was met:

1. Demonstration of the safety of HDR brachytherapy for previously irradiated lesions of the spine and pelvis.
 - a. Both acute and late (1 year post-treatment) toxicity will be evaluated. Neurological evaluation and ambulation assessment will be carried out prior to treatment to serve as a baseline. During each subsequent follow up visit, patients will be asked to provide evaluations of their symptoms. The primary expected toxicities are musculoskeletal and neurological. Grade 2 toxicity is almost always self limiting and by definition manageable with medications, not requiring invasive procedures. Thus grade 2 toxicities will not be considered as serious adverse events.
2. Efficacy of HDR brachytherapy for relief of pain
 - a. Patients will be assessed prior to treatment and at each followup visit using the standardized 11-point (0-10) Numeric Rating Scale (NRS-11). Descriptive statistics regarding time to, degree of, and duration of relief from pain (if any) will be reported in summary form.
3. Disease-free progression at the treatment site.
 - a. Imaging studies and clinical assessment performed at each followup date will be used to assess degree of response; tumor control will be defined for this study as the lack of tumor progression at the treated site, where progression may consist of an increase in maximal dimension of the tumor by $\geq 20\%$, compromise of the spinal cord/cauda equina and/or exiting spinal nerves (assessed clinically or radiographically), or both.

The following instruments will be used in the evaluation of toxicities:

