14. BIOSTATISTICS

This is a pilot interventional study to evaluate the feasibility of high dose rate (HDR) brachytherapy using image-guided navigational techniques as salvage therapy for previously treated lesions of the spine. The primary outcome that we wish to assess is the reproducibility of the treatment plan parameters; secondary outcomes include toxicity, relief of pain, and local disease progression.

In terms of technical feasibility, a patient is regarded as being successfully treated if the target D90 is $\geq 80\%$ AND the cord/cauda max dose is 8 Gy. To this end we will enroll 20 patients and declare the procedure feasible if at least 15 patients can be successfully treated. For this decision rule we have the following probability table:

True feasibility rate	55%	60%	65%	70%	75%	80%	85%	90%
Probability of declaring feasible	0.055	0.126	0.245	0.416	0.617	0.804	0.933	0.989

We believe this procedure will be quite safe for patients; a previous study from Japan [Seichi 1999] showed serious toxicity rates of approximately 3%, and we anticipate ours will be even lower. Among the 20 patients we expect to see less than 2 adverse events. In the event that a second serious adverse event (\geq Grade 3, or as otherwise defined above in Section 11.0) occurs, this protocol will be immediately halted and the investigator will carefully examine the cases with the assistance of the co-principal investigator and at least one investigator from both Medical Physics and Radiology and review the protocol (to be either terminated or modified in order to proceed further). Self-reported pain scores will be recorded and descriptive statistics regarding time to, degree of, and duration of relief from pain (if any) will be summarized numerically and/or graphically. In-field progression-free probability will be estimated using Kaplan-Meier estimation.

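### Required safety capture ends at about 11 months to 1 year per patient in a 4-year study, so a related severe late event in an early patient need not be recorded or counted toward the halt rule while later patients are still being treated

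*Combined protocol and SAP*

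**What the plan says.** Section 1.0 sets size and duration: "Twenty patients will be entered into this protocol which is expected to take 4 years to complete". It does not say whether the 4 years include follow-up of the last patient.

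Section 10.0 places visits at 2 months, "then at 3 month (+/- 2 weeks) intervals until approximately 11 months of follow up", which gives about 2, 5, 8 and 11 months. The study calendar schedules adverse event assessment at those visits. On complications the section says: "Treatment complications will be monitored in terms of radiation related toxicity during post-procedure recovery and during followup visits". It then closes the period: "Follow up after 1 year will be performed as per standard clinical practice with no further protocol obligations".

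Section 11.0 defines late toxicity as running from 90 days to 1 year, and Section 12.0 agrees: "Both acute and late (1 year post-treatment) toxicity will be evaluated". Section 11.0 also singles out neurologic and musculoskeletal toxicity (myelitis, pathologic fracture) as the potentially serious kinds, says they tend to come late, and makes any such toxicity of grade 3 or higher an SAE.

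Section 14 sets the halt rule, which begins "In the event that a second serious adverse event" and leads to an immediate halt and case review. Neither this rule, nor the accrual stop at a 10% toxicity level in Section 4.1, nor SAE reporting in Section 17.2 states an end date.

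**The concern.** The halt rule counts events that the protocol itself expects to be late, but the duty to look for them ends at about 1 year while enrolment may go on for two or three more. Suppose a patient treated early develops a related grade 3 myelitis or fracture at month 14 or 20. Nothing requires the study to find it, record it, report it or count it. Two investigators could reasonably disagree on whether it counts: one relying on the end of obligations in Section 10.0, the other on the open-ended rule in Section 14.

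At stake is whether later patients could be treated without a review that two known severe events would have triggered, and whether the final safety report would leave those events out. Safety, covering acute and late effects, is a stated secondary objective in Section 2.0. This is a separate matter from the small difference between an 11-month last visit and a 1-year late-toxicity window: using 1 year throughout would leave the gap open.

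**Working it through.** **What the plan calculates.** Its only operating-characteristic table is for feasibility (at least 15 successes in 20). The exact binomial tail reproduces all eight entries, for example 0.617 at 75% and 0.804 at 80%. That table does not bear on this point. The documents give no such table for the halt rule and no figure for time at risk, so what follows is an illustration.

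**Inputs from the documents.** 20 patients; 4 years in total; last visit at about 11 months; protocol obligations end at 1 year.

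**Assumptions.** Accrual is even over A months. A = 48 if the 4 years are all accrual; A = 48 − 11 = 37 if they include the last patient's follow-up. Survival is exponential with median m = 6, 12 or 24 months. The documents give no survival figure, so these medians only span a range.

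**Step 1: patients past 1 year before accrual closes, no deaths.** Patient i enters at (i − 0.5)A/20, leaving xᵢ = A − (i − 0.5)A/20 months until accrual closes. Count xᵢ > 12.
- A = 37: 14 patients, the last only just past (12.025 months).
- A = 48: 15 patients.

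**Step 2: share of patient-months after 1 year, no deaths.** Share = Σ max(xᵢ − 12, 0) / Σ xᵢ.
- A = 37: 168.7/370 = 46%.
- A = 48: 270/480 = 56%.

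**Step 3: the same share with deaths.** With λ = ln 2/m, expected time at risk per patient is (1 − e^(−λx))/λ. The part after 1 year is (e^(−12λ) − e^(−λx))/λ for x > 12. The number alive when obligations end is the count from step 1 times e^(−12λ), which is 0.25, 0.50 or 0.71.

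| Median survival | Share after 1 year, A = 37 | Share after 1 year, A = 48 | Alive at 1 year before accrual closes |
|---|---|---|---|
| 6 months | 19.6/133.3 = 14.7% | 24.8/142.1 = 17.5% | 14 × 0.25 = 3.5 to 15 × 0.25 = 3.75 |
| 12 months | 55.0/203.4 = 27.0% | 75.3/229.3 = 32.8% | 14 × 0.50 = 7.0 to 15 × 0.50 = 7.5 |
| 24 months | 95.1/267.1 = 35.6% | 139.0/317.9 = 43.7% | 14 × 0.707 = 9.9 to 15 × 0.707 = 10.6 |

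**Sensitivity to the cut-off.** Cutting at the last visit (11 months) instead of 1 year raises the shares to 18%-20%, 31%-36% and 39%-47%, and the no-death share to 49%-59%. The 1-year cut is used here because that is where Section 10.0 ends the obligation.

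**The case against.** The strongest reply is that the 1-year window is a stated choice in a 20-patient feasibility pilot with safety as a secondary objective, and that the sentence ending obligations sits among text about visits, imaging and billing. That stands: the 1-year definition of late toxicity is consistent and need not change. What it does not settle is whether a later related SAE counts while patients are still being enrolled.

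Three stronger readings are tempting, and the documents do not support them.

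- A reader might infer that a later event can never reach the halt rule. The halt rule, the accrual stop and SAE reporting have no end date, so an event noticed in clinic could be counted. The accurate finding is that its capture and counting are not required.
- A reader might take the cord figure in Section 3.0, "with an attendant 5% risk of myelopathy at 5 years", as the risk in this trial. It is background for a 50 Gy cord limit in otherwise healthy patients treated for cure. The protocol's own expectations (neurological toxicity of about 5% in Section 3.4, severe toxicity below 10% in Section 11.0) have no time horizon. Even if 5% at 5 years is borrowed with a constant hazard, 48-month accrual and no deaths, the chance of seeing a second event by year 4 moves only from 0.014 (1-year cap) to 0.061 (no cap).
- A reader might conclude that the longest-followed patients carry most of the safety information. In every survival scenario above, less than half of the time at risk falls after 1 year. The 56% figure needs no deaths at all. Patient-months are also not events.

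It is also fair to say that patients may not return. Section 1.0 says only that later follow-up is as clinically indicated, and Section 10.0 already allows telephone visits and outside imaging. Chart review will therefore miss some events.

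**Conclusion.** The point holds as a gap in required capture. After 1 year the plan does not require a related grade 3 or higher late event to be recorded or counted, although enrolment may still be open and the halt rule has no time limit. Under even accrual over 37 to 48 months, about 4, 7 to 8, or 10 to 11 patients would be alive and past required capture at some time before accrual closes, at assumed median survival of 6, 12 or 24 months. The matching share of time at risk is about 15%-18%, 27%-33% or 36%-44%. These figures rest on assumed accrual and survival. They measure unobserved time, not missed events, which the documents do not allow one to estimate. The change is worth making because it bears directly on the halt rule and costs little.

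**What to change.** In Sections 10.0, 11.0 and 14, state the following:

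- While enrolment and treatment are open, any grade 3 or higher neurologic or musculoskeletal event with at least a possible relation to protocol treatment, found in routine care after 1 year, is abstracted from the chart by the research study assistant already assigned in Section 16.0. It is reported under Section 17.2 and counted in the existing second-SAE review.
- After the last patient is treated, such events are reported only, because a halt would then protect no one.
- The 1-year definition of late toxicity stays. Later events are listed separately, with each patient's follow-up time.

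The relatedness condition, taken from Sections 2.0 and 11.0, matters: without it, a fracture or cord compression from tumour progression could trigger the halt. No study visits are added and the two-event threshold is unchanged.

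The cost is amendment wording and periodic chart review. The longer exposure somewhat raises the chance of triggering the two-event rule. Capture after 1 year will be incomplete because patients may not return, so the later events should be reported as a minimum count.
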